14.11. Appendix 11: Abbreviations & Trade Marks

14.11.1. Abbreviations

Abbreviation	Description
ACQ	Asthma Control Questionnaire
ADaM	Analysis Data Model
AE	Adverse Event
A&R	Analysis and Reporting
CDISC	Clinical Data Interchange Standards Consortium
CI	Confidence Interval
CPMS	Clinical Pharmacology Modelling & Simulation
CS	Clinical Statistics
CSR	Clinical Study Report
DBF	Database Freeze
DBR	Database Release
DOB	Date of Birth
DP	Decimal Places
eCRF	Electronic Case Record Form
ECG	Electrocardiogram
ED	Emergency Department
GSK	GlaxoSmithKline
ICH	International Conference on Harmonization
IDMC	Independent Data Monitoring Committee
IDSL	Integrated Data Standards Library
IP	Interventional Product
ITT	Intent-To-Treat
MMRM	Mixed Model Repeated Measures
NP	Nasal Polyps
OCS	Oral Corticosteroid
PCI	Potential Clinical Importance
PD	Pharmacodynamic
PDMP	Protocol Deviation Management Plan
PK	Pharmacokinetic
PnIF	Peak Nasal Inspiratory Flow
PP	Per Protocol
PopPK	Population PK
PopPKPD	Pharmacokinetic / Pharmacodynamic
QC	Quality Control
QTcF	Frederica's QT Interval Corrected for Heart Rate
QTcB	Bazett's QT Interval Corrected for Heart Rate
RAP	Reporting & Analysis Plan
RAMOS	Randomization & Medication Ordering System
SAC	Statistical Analysis Complete
SC	Subcutaneous
SDSP	Study Data Standardization Plan

CONFIDENTIAL

2020N427698_00

205687

Abbreviation	Description
SDTM	Study Data Tabulation Model
SF-36	Short Form-36
SNOT-22	Sino-Nasal Outcome Test -22
SoC	Standard of Care
SOP	Standard Operation Procedure
TA	Therapeutic Area
TFL	Tables, Figures & Listings
UPSIT	University of Pennsylvania Smell Identification Test
VAS	Visual Analogue Scale
WPAI	Work Productivity and Impairment

14.11.2. Trademarks

Trademarks of the GlaxoSmithKline Group of Companies
NONE

Trademarks not owned by the GlaxoSmithKline Group of Companies
NONMEM
SAS
WinNonlin

14.12. Appendix 12: List of Data Displays

14.12.1. Data Display Numbering

The following numbering will be applied for RAP generated displays:

Section	Tables	Figures
Study Population	1.1 to 1.22	1.1
Efficacy	2.1 to 2.69	2.1 to 2.25
Safety	3.1 to 3.68	3.1 to 3.3
Population Pharmacokinetic (PopPK)	4.1 to 4.7	4.1 to 4.9
Pharmacokinetic / Pharmacodynamic (PopPKPD)	5.1 to 5.4	5.1 to 5.8
Exposure-Efficacy		6.1 to 6.4
Section	Listings	
ICH and Other Listings	1 to 52	

14.12.2. Mock Example Shell Referencing

Non IDSL specifications will be referenced as indicated and if required example mock-up displays provided in [Appendix 13](#): Example Mock Shells for Data Displays.

Section	Figure	Table	Listing
Study Population	POP_Fn	POP_Tn	POP_Ln
Efficacy	EFF_Fn	EFF_Tn	EFF_Ln
Safety	SAFE_Fn	SAFE_Tn	SAFE_Ln
Population Pharmacokinetic (PopPK)	POPPK_Fn	POPPK_Tn	POPPK_Ln
Pharmacokinetic / Pharmacodynamic (PopPKPD)	POPPKPD_Fn	POPPKPD_Tn	POPPKPD_Ln
Efficacy Exposure	EE_Fn	EE_Tn	EE_Ln

NOTES:

- Non-Standard displays are indicated in the 'IDSL/Shell' or 'Programming Notes' column with an associated reference.'

14.12.3. Deliverables

Delivery Priority ^[1]	Description
SAC [1]	Headline Results
SAC [2]	Final Statistical Analysis Complete

NOTES:

[1] Indicates priority (i.e. order) in which displays will be generated for the reporting effort

CONFIDENTIAL

205687

14.12.4. Study Population Tables

Study Population Tables					
No.	Population	IDSL / Example Shell	Title	Programming Notes	Deliverable [Priority]
Subject Disposition					
1.1.	ITT	SD1	Summary of Treatment Status and Reasons for Discontinuation of Study Treatment	ICH E3	SAC [1]
1.2.	ITT	SHELL	Summary of Time On- and Off-Treatment by Withdrawal Scenario	Withdrawal scenarios are detailed in Section 14.7.2.3. Add footnote to indicate exclusion of data from the follow-up period after Week 52	SAC [2]
1.3.	ITT	ES1	Summary of Subject Disposition (Week 52)	ICH E3, FDAAA, EudraCT	SAC [1]
1.4.	FU	ES1	Summary of Subject Disposition (Follow-Up Period after Week 52)		SAC [2]
1.5.	FU	SHELL	Summary of Duration of Time in Follow-Up Period after Week 52		SAC [2]
1.6.	ENROLLED	ES6	Summary of Screening and Run-In Status and Reasons for Screen and Run-In Failures	Journal Requirements	SAC [2]
1.7.	ENROLLED	NS1/SHELL	Summary of Number of Subjects by Region, Country and Centre	EudraCT/Clinical Operations Add in column for region, add a total for each region and a total for each country.	SAC [2]
Protocol Deviation					
1.8.	ITT	DV1	Summary of Important Protocol Deviations	ICH E3	SAC [2]
Population Analysed					
1.9.	ENROLLED	SP1	Summary of Study Populations	IDSL	SAC [1]
1.10.	Randomised	SP2A	Summary of Exclusions from the Intent-to-Treat and Safety Populations	IDSL	SAC [2]

CONFIDENTIAL

205687

Study Population Tables					
No.	Population	IDSL / Example Shell	Title	Programming Notes	Deliverable [Priority]
Demographic and Baseline Characteristics					
1.11.	ITT	DM1	Summary of Demographic Characteristics	ICH E3, FDAAA, EudraCT	SAC [1]
1.12.	ENROLLED	DM11	Summary of Age Ranges	EudraCT	SAC [2]
1.13.	ITT	DM5	Summary of Race and Racial Combinations	ICH E3, FDA, FDAAA, EudraCT	SAC [2]
1.14.	ITT	Shell	Summary of Nasal Polyps Disease History and Characteristics	Include Disease Duration (years/months); Number of previous surgeries; Number of Courses of OCS for NP in previous 12 months. Baseline Nasal Polyps endoscopy score (centrally read and investigator read); Baseline SNOT-22.	SAC [1]
1.15.	ITT	Shell	Summary of Previous Exacerbation History	To include separate summary of information for Asthma and COPD Exacerbation History	SAC [2]
Medical Conditions					
1.16.	ITT	MH4	Summary of Past Medical Conditions	ICH E3	SAC [2]
1.17.	ITT	MH4	Summary of Current Medical Conditions	ICH E3	SAC [2]
Prior and Concomitant Medications					
1.18.	ITT	CM1	Summary of Medications Started Prior to Treatment	ICH E3; ATC classification to be displayed for combination medications (not for individual ingredients)	SAC [2]
1.19.	ITT	CM1	Summary of Concomitant Medications Started During Treatment	ICH E3; ATC classification to be displayed for combination medications (not for individual ingredients). Footnote: Includes medications started after first dose and before last dose + 28 days.	SAC [2]

CONFIDENTIAL

205687

Study Population Tables					
No.	Population	IDSL / Example Shell	Title	Programming Notes	Deliverable [Priority]
1.20.	ITT	CM1	Summary of Systemic Corticosteroids Started During Treatment	Footnote: Includes medications started after first dose and before last dose + 28 days.	SAC [2]
Exposure					
1.21.	ITT	SHELL	Summary of Exposure (Therapeutic Coverage) to Interventional Product	ICH E3 Range of Exposure (months): 1-<3, 3-<6, 6-<9, 9-<12, >=12Also add subject years exposure	SAC [2]
1.22.	ITT	SHELL	Summary of Number of Treatments Administered		SAC [2]

14.12.5. Study Population Figures

Study Population Figures					
No.	Population	IDSL / Example Shell	Title	Programming Notes	Deliverable [Priority]
Subject Disposition					
1.1.	ITT	SHELL	Subject Withdrawal from Interventional Product	Footnote: Kaplan-Meier estimates of time to withdrawal from IP. Subjects are represented from Day 1 to Day of withdrawal from IP	SAC [2]

CONFIDENTIAL

205687

14.12.6. Efficacy Tables

Efficacy: Tables					
No.	Population	IDSL / Example Shell	Title	Programming Notes	Deliverable [Priority]
Co-Primary Endpoints					
2.1.	ITT	SHELL	Summary of Total Endoscopic Nasal Polyps Score (Centrally Read)	Footnote: Includes data reported up to Week 52 Include actual scores and change from baseline Based on the primary analysis dataset	SAC [1]
2.2.	ITT	SHELL	Analysis of Median Change from Baseline Total Endoscopic Nasal Polyps Score (Centrally Read) at Week 52		SAC [1]
2.3.	ITT	SHELL	Sensitivity Analysis of Median Change from Baseline Total Endoscopic Nasal Polyps Score (Centrally Read) at Week 52: Assigned Worst Possible Score Across All Subjects for Missing and Worst Observed Score for Surgery/Sinuplasty		SAC [2]
2.4.	ITT	SHELL	Sensitivity Analysis of Median Change from Baseline Total Endoscopic Nasal Polyps Score (Centrally Read) at Week 52: Assigned Worst Possible Score Across All Subjects for Missing and Surgery/Sinuplasty		SAC [2]
2.5.	PP	SHELL	Supplementary Analysis of Median Change from Baseline Total Endoscopic Nasal Polyps Score (Centrally Read) at Week 52: Per-Protocol Population		SAC [2]
2.6.	ITT	SHELL	Subgroup Analysis of Median Change from Baseline Total Endoscopic Nasal Polyps Score (Centrally Read) at Week 52 by Participants with Asthma		SAC [2]
2.7.	ITT	SHELL	Subgroup Analysis of Median Change from Baseline Total Endoscopic Nasal Polyps Score (Centrally Read) at Week 52 by Aspirin Exacerbated Respiratory Disease (AERDS)		SAC [2]

CONFIDENTIAL

205687

Efficacy: Tables					
No.	Population	IDSL / Example Shell	Title	Programming Notes	Deliverable [Priority]
2.8.	ITT	SHELL	Subgroup Analysis of Median Change from Baseline Total Endoscopic Nasal Polyps Score (Centrally Read) at Week 52 by Number of Previous Surgeries		SAC [2]
2.9.	ITT	SHELL	Subgroup Analysis of Median Change from Baseline Total Endoscopic Nasal Polyps Score (Centrally Read) at Week 52 by Baseline Blood Eosinophil Categories		SAC [2]
2.10.	ITT	SHELL	Subgroup Analysis of Median Change from Baseline Total Endoscopic Nasal Polyps Score (Centrally Read) at Week 52 by Region		SAC [2]
2.11.	ITT	SHELL	Subgroup Analysis of Median Change from Baseline Total Endoscopic Nasal Polyps Score (Centrally Read) at Week 52 by Age		SAC [2]
2.12.	ITT	SHELL	Subgroup Analysis of Median Change from Baseline Total Endoscopic Nasal Polyps Score (Centrally Read) at Week 52 by Gender		SAC [2]
2.13.	ITT	SHELL	Subgroup Analysis of Median Change from Baseline Total Endoscopic Nasal Polyps Score (Centrally Read) at Week 52 by Race		SAC [2]
2.14.	ITT	SHELL	Summary of Individual VAS Symptom Scores	Footnote: Includes data reported up to Week 52 Subheaders: Nasal Obstruction, Nasal Discharge, Mucus in Throat, Loss of Smell, Facial Pain	SAC [2]
2.15.	ITT	SHELL	Analysis of Median Change from Baseline Nasal Obstruction VAS Score (Weeks 49-52)		SAC [1]

CONFIDENTIAL

205687

Efficacy: Tables					
No.	Population	IDSL / Example Shell	Title	Programming Notes	Deliverable [Priority]
2.16.	ITT	SHELL	Sensitivity Analysis of Median Change from Baseline Nasal Obstruction VAS Score (Weeks 49-52):- Assigned Worst Possible Mean Across All Subjects for Missing and Worst Observed Mean for Surgery/Sinuplasty		SAC [2]
2.17.	ITT	SHELL	Sensitivity Analysis of Change from Baseline Nasal Obstruction VAS Score (Weeks 49-52): Assigned Worst Possible Mean Across All Subjects for Missing and Surgery/Sinuplasty		SAC [2]
2.18.	PP	SHELL	Supplementary Analysis of Median Change from Baseline Nasal Obstruction VAS Score (Weeks 49-52): Per-Protocol Population		SAC [2]
2.19.	ITT	SHELL	Subgroup Analysis of Median Change from Baseline Nasal Obstruction VAS Score (Weeks 49-52) by Subjects with Asthma		SAC [2]
2.20.	ITT	SHELL	Subgroup Analysis of Median Change from Baseline Nasal Obstruction VAS Score (Weeks 49-52) by Aspirin Exacerbated Respiratory Disease (AERDS)		SAC [2]
2.21.	ITT	SHELL	Subgroup Analysis of Median Change from Baseline Nasal Obstruction VAS Score (Weeks 49-52) by Number of Previous Surgeries		SAC [2]
2.22.	ITT	SHELL	Subgroup Analysis of Median Change from Baseline Nasal Obstruction VAS Score (Weeks 49-52) by Baseline Blood Eosinophil Categories		SAC [2]
2.23.	ITT	SHELL	Subgroup Analysis of Median Change from Baseline Nasal Obstruction VAS Score (Weeks 49-52) by Region		SAC [2]
2.24.	ITT	SHELL	Subgroup Analysis of Median Change from Baseline Nasal Obstruction VAS Score (Weeks 49-52) by Age		SAC [2]
2.25.	ITT	SHELL	Subgroup Analysis of Median Change from Baseline Nasal Obstruction VAS Score (Weeks 49-52) by Gender		SAC [2]

CONFIDENTIAL

205687

Efficacy: Tables					
No.	Population	IDSL / Example Shell	Title	Programming Notes	Deliverable [Priority]
2.26.	ITT	SHELL	Subgroup Analysis of Median Change from Baseline Nasal Obstruction VAS Score (Weeks 49-52) by Race		SAC [2]
Secondary Endpoints					
2.27.	ITT	SHELL	Analysis of Time to First Nasal Surgery	Footnote: Includes data reported up to Week 52	SAC [1]
2.28.	ITT	SHELL	Sensitivity Analysis of Time to First Nasal Surgery: Tipping Point Analysis	Footnote: Includes data reported up to Week 52	SAC [2]
2.29.	ITT	SHELL	Summary of Overall VAS Score	Footnote: Includes data reported up to Week 52	SAC [1]
2.30.	ITT	SHELL	Analysis of Median Change from Baseline Overall VAS Score (Weeks 49-52)		SAC [1]
2.31.	ITT	SHELL	Summary of SNOT-22 Total Score	Footnote: Includes data reported up to Week 52	SAC [1]
2.32.	ITT	SHELL	Analysis of Median Change from Baseline SNOT-22 at Week 52		SAC [1]
2.33.	ITT	SHELL	Summary and Analysis of Proportion of Subjects Requiring Systemic Steroids for Nasal Polyps up to Week 52	Footnote: Courses of systemic steroids separated by <7 days are considered a continuation of the same course Include n (%) with 0 vs ≥1 and 0, 1, 2, etc courses and total number of courses	SAC [1]
2.34.	ITT	SHELL	Subgroup Analysis of Proportion of Subjects Requiring Systemic Steroids for Nasal Polyps up to Week 52 by Participants with Asthma	Footnote: Courses of systemic steroids separated by <7 days are considered a continuation of the same course Include n (%) with 0 vs ≥1 and 0, 1, 2, etc courses and total number of courses	SAC [2]

CONFIDENTIAL

205687

Efficacy: Tables					
No.	Population	IDSL / Example Shell	Title	Programming Notes	Deliverable [Priority]
2.35.	ITT	SHELL	Summary of Composite VAS Scores	Footnote: Includes data reported up to Week 52 Subheaders: Composite - Nasal Symptoms [1] and Composite - Nasal Symptoms and Facial Pain [2] Footnote: [1] Composite - Nasal Symptoms includes nasal obstruction, nasal discharge, mucus in the throat and loss of smell [2] Composite - Nasal Symptoms and Facial Pain includes nasal obstruction, nasal discharge, mucus in the throat and loss of smell and facial pain	SAC [1]
2.36.	ITT	SHELL	Analysis of Median Change from Baseline Composite VAS Score - Nasal Symptoms (Weeks 49-52)		SAC [1]
2.37.	ITT	SHELL	Analysis of Median Change from Baseline Loss of Smell VAS Score (Weeks 49-52)		SAC [1]
2.38.	ITT	SHELL	Summary of P-values for Treatment Comparisons Adjusted for Multiplicity According to Hierarchy of Endpoints		SAC [1]
Other Endpoints					
2.39.	ITT	SHELL	Summary of Total Endoscopic Nasal Polyps Score (Investigator Read)	Footnote: Includes data reported up to Week 52 Programming Note: summaries from dataset with assigned values for subjects with surgery/missing data	SAC [2]
2.40.	ITT	SHELL	Summary and Analysis of Total Endoscopic Nasal Polyps Score (Centrally Read) Responders	Footnote: Includes data reported up to Week 52	SAC [2]

CONFIDENTIAL

205687

Efficacy: Tables					
No.	Population	IDSL / Example Shell	Title	Programming Notes	Deliverable [Priority]
2.41.	ITT	SHELL	Analysis of Median Change from Baseline VAS Scores: Nasal Discharge, Mucus in Throat, Facial Pain (Weeks 49-52)		SAC [2]
2.42.	ITT	SHELL	Analysis of Median Change from Baseline Composite VAS Score - Nasal Symptoms and Facial Pain (Weeks 49-52)		SAC [2]
2.43.	ITT	SHELL	Summary and Analysis of SNOT-22 Responders at Week 52	Footnote: Includes data reported up to Week 52	SAC [2]
2.44.	ITT	SHELL	Summary of SNOT-22 Domain Scores	Footnote: Includes data reported up to Week 52 Subheaders: Nasal, Non-nasal symptoms, Ear/facial symptoms, Sleep, Fatigue, Emotional consequences Programming Note: summaries from dataset with assigned values for subjects with surgery/missing data	SAC [2]
2.45.	ITT	SHELL	Summary and Analysis of Need for Surgery to Week 52	Footnote: Includes data reported up to Week 52	SAC [2]
2.46.	ITT	SHELL	Summary of Frequency and Rate of Nasal Surgery	Include n (%) with 0, 1, 2, etc surgeries and crude rate Footnote: Includes data reported up to Week 52	SAC [2]
2.47.	ITT	SHELL	Time to First Inclusion on Waiting List for Nasal Polyps Surgery	Footnote: Includes data reported up to Week 52	SAC [2]
2.48.	ITT	SHELL	Summary of Subjects Placed on Waiting List for Surgery to Week 52	Footnote: Includes data reported up to Week 52	SAC [2]
2.49.	ITT	SHELL	Summary of University of Pennsylvania Smell Identification Test (UPSIT)	Footnote: Includes data reported up to Week 52 Footnote: performed in UK, US and Canada only	SAC [2]

CONFIDENTIAL

205687

Efficacy: Tables					
No.	Population	IDSL / Example Shell	Title	Programming Notes	Deliverable [Priority]
2.50.	ITT	SHELL	Analysis of Median Change from Baseline University of Pennsylvania Smell Identification Test (UPSIT)	Footnote: performed in UK, US and Canada only	SAC [2]
2.51.	ITT	SHELL	Summary of Peak Nasal Inspiratory Flow (PNIF)	Include actual and change from baseline Footnote: Includes data reported up to Week 52 Programming Note: summaries from dataset with assigned values for subjects with surgery/missing data	SAC [2]
2.52.	ITT	SHELL	Summary of Total Prednisolone-equivalent OCS Use for Nasal Polyps (mgs per year)	Footnote: Includes data reported up to Week 52	SAC [2]
2.53.	ITT	SHELL	Summary of Days on Systemic Steroids for Nasal Polyps	Footnote: Includes data reported up to Week 52 Include days on therapy and percentage of days on therapy	SAC [2]
2.54.	ITT	SHELL	Time to First Course of Systemic Steroids for Nasal Polyps	Footnote: Includes data reported up to Week 52	SAC [2]
2.55.	ITT	SHELL	Analysis of Time to First Nasal Surgery or Course of Systemic Steroids for Nasal Polyps	Footnote: Includes data reported up to Week 52	SAC [2]
2.56.	ITT	SHELL	Summary of Number of Courses of Antibiotics	Footnote: Includes data reported up to Week 52 Footnote: Courses of antibiotics separated by <7 days are considered a continuation of the same course Include n (%) with 0 vs ≥ 1 and 0, 1, 2, courses and total number of courses	SAC [2]
2.57.	ITT	SHELL	Summary of On-Treatment Blood Eosinophils (GI/L)	Include absolute and ratio to baseline values	SAC [2]

CONFIDENTIAL

205687

Efficacy: Tables					
No.	Population	IDSL / Example Shell	Title	Programming Notes	Deliverable [Priority]
2.58.	ITT	SHELL	Analysis of On-Treatment Blood Eosinophils (GI/L) Ratio Compared to Baseline Mixed Model Repeated Measures		SAC [2]
Other Endpoints – Health Economics/Medical Resource Utilisation					
2.59.	ITT	SHELL	Summary of SF-36 Domain Scores and Component Summary Scores	
Include 8 domain scores bodily pain, general health, mental health, physical functioning, role emotional, role physical, social functioning and vitality and Mental and Physical Component Summary scores.
 
Include actual and change from baseline (b) (4)
 
Footnote: Includes data reported up to Week 52
 
Programming Note: summaries from dataset with assigned values for subjects with surgery/missing data
	SAC [2]
2.60.	ITT	SHELL	Summary of Work Productivity and Activity Impairment Questionnaire (WPAI)	
Footnote: Includes data reported up to Week 52
 
Include only summary variables
	SAC [2]
Other Endpoints – Participants with Asthma					
2.61.	ITT	SHELL	Summary of ACQ-5 in Participants with Asthma	
Include actual and change from baseline
 
Footnote: Includes data reported up to Week 52
 
Programming Note: summaries from dataset with assigned values for subjects with surgery/missing data
	SAC [2]

CONFIDENTIAL

205687

Efficacy: Tables					
No.	Population	IDSL / Example Shell	Title	Programming Notes	Deliverable [Priority]
2.62.	ITT	SHELL	Summary of Frequency of Clinically Significant Asthma Exacerbations in Participants with Asthma	Provide n (%) with 0 vs ≥ 1 and 0, 1, 2 etc exacerbations and total number of exacerbations Footnote: Includes data reported up to Week 52	SAC [2]
Other Endpoints – Maintenance of Response Following Cessation of Interventional Product (Follow-Up Period After Week 52)					
2.63.	FU	SHELL	Summary of Total Endoscopic Nasal Polyps Score (Centrally Read) for Subjects in the Follow-Up Period After Week 52	Include actual and change from baseline Programming Note: summaries from dataset with assigned values for subjects with surgery/missing data	SAC [2]
2.64.	FU	SHELL	Summary of Individual VAS Symptom Scores for Subjects in the Follow-Up Period After Week 52	Include actual and change from baseline Include nasal obstruction, nasal discharge, mucus in throat, loss of smell, facial pain, overall VAS score Programming Note: summaries from dataset with assigned values for subjects with surgery/missing data	SAC [2]
2.65.	FU	SHELL	Summary of SNOT-22 for Subjects in the Follow-Up Period After Week 52	Include actual and change from baseline Programming Note: summaries from dataset with assigned values for subjects with surgery/sinuplasty/missing data	SAC [2]
2.66.	FU	SHELL	Time to First Nasal Surgery for Subjects in the Follow-Up Period After Week 52		SAC [2]

CONFIDENTIAL

205687

Efficacy: Tables					
No.	Population	IDSL / Example Shell	Title	Programming Notes	Deliverable [Priority]
2.67.	FU	SHELL	Summary of Number of Courses of Systemic Steroids for Subjects in the Follow-Up Period After Week 52	Footnote: Courses of systemic steroids separated by less than 7 days are considered a continuation of the same course	SAC [2]
2.68.	FU	SHELL	Summary of Total Prednisolone-equivalent OCS Use for Nasal Polyps (mgs per year)		SAC [2]
2.69.	FU	SHELL	Summary of Blood Eosinophils (GI/L) for Subjects in the Follow-up Period After Week 52		SAC [2]

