4. ANALYSIS POPULATIONS

Population	Definition / Criteria	Analyses Evaluated
Enrolled	
 All participants enrolled and for whom a record exists on the study database. 	Reasons for screen and run-in failures
Randomized	
 All randomized participants 	Study population
Intent-To-Treat (ITT)	
 All randomized participants who take at least 1 dose of study treatment. Data will be analysed according to randomised treatment arm. 	Subject disposition Efficacy endpoints
Safety	
 All randomized participants who take at least 1 dose of study treatment. Data will be analysed according to actual treatment received for more than 50% of treatment administrations (see Section 14.6.2). 	Safety endpoints
Per-Protocol (PP) ^[1]	
 All participants in the ITT population who have not been identified as protocol deviators with respect to criteria that are considered to impact the primary efficacy analysis. Protocol deviations that would exclude participants from the PP population are defined in Appendix 1: Protocol Deviation Management and Definitions for Per-Protocol Population 	Supplementary analyses of co-primary endpoints
Pharmacokinetic (PK) ^[1]	All participants in the ITT population for whom at least one PK sample was obtained, analysed and measurable.	Pharmacokinetic endpoints
Follow-up after	
 Participants in the ITT population who participate in the 	Efficacy/safety

Population	Definition / Criteria	Analyses Evaluated
Week 52 (FU) [1]	'No treatment follow-up' period after Visit 15. 
 Data will be summarised according to randomised treatment arm. 	endpoints

Refer to [Appendix 12](#): List of Data Displays which details the population used for each display.

[1] Analysis population not defined in protocol, added for clarification of analysis requirements.

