7.5. Maintenance of response

The following endpoints will be summarised for the subset of participants who entered the no-treatment 6-month follow up period after Week 52. All data reported by these participants for the duration of their time in the study will be included in these summaries, this will include data reported prior to entering the follow-up period (whether or not the subject had prematurely discontinued from interventional product during that time) and data reported after entering the follow-up period.

- Change from baseline in total endoscopic NP score (centrally read)
- Change from baseline in mean nasal obstruction VAS score
- Change from baseline in mean individual VAS symptom score for nasal discharge, mucus in throat, loss of smell and facial
- Change from baseline in mean overall VAS symptom score
- Proportion of subjects requiring systemic steroids for nasal polyps
- Number of mgs per year of prednisolone-equivalent OCS dose
- Change from baseline in SNOT-22 total score
- Time to first nasal surgery
- Time to first inclusion on waiting list for NP surgery

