14.6.4. Change from Baseline

Definition	Reporting Details
Change from Baseline	= Post-Dose Visit Value – Baseline
% Change from Baseline	= 100 x [(Post-Dose Visit Value – Baseline) / Baseline]
Ratio to Baseline ^[1]	= Post-Dose Visit Value / Baseline

NOTES: Refer to Section 5.2 for definition of Baseline. Unless otherwise stated, if Baseline or the Post-Dose value is missing the result will be set to missing.

[1] For log_e transformed data Ratio to Baseline is the back transformed change from baseline value

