14.6.5. Efficacy

Assigning the worst score for subjects with surgery or missing data
Relevant efficacy endpoints

 Subjects who undergo surgery/sinuplasty will have their worst observed score (or worst observed 4-week mean) assigned for all subsequent visits (or 4-week periods) following surgery/sinuplasty. The assigned value will be the worst observed value from baseline up to before the surgery/sinuplasty. Assessments taking place on the same day as surgery/sinuplasty are assumed to have been carried out before the surgery/sinuplasty. Subjects who have not experienced surgery/sinuplasty and have missing values due to study withdrawal, will have their worst observed score (or worst observed 4-week mean) assigned for all missing visits (or 4-week periods) following study withdrawal. The assigned value will be the worst observed value from baseline up until study withdrawal. Subjects with missing data for other reasons will have their worst observed score (or worst observed 4-week mean) prior to the missing visit (or missing 4-week period) assigned.
Total Endoscopic Nasal Score
Responder

 A responder will be defined as a participant with a ≥1-point improvement from baseline in total endoscopic nasal score (centrally read). Participants with no improvement/worsening or with missing data will be considered a non-responder for analysis.
VAS scores (individual and composite)
Individual VAS Scores

 VAS scores are captured electronically using an eDiary. participants indicate their response on a line CCI - This section contained Clinical Outcome Assessment data collection questionnaires or indices, which are protected by third party copyright laws and therefore have been excluded. The final VAS scores for inclusion in summary and analysis tables will be derived from the electronically captured score by CCI.
Change from baseline categories

 The baseline scores will be calculated as the mean of the scores reported between the 7 days prior to the first dose. The scores for each 4-week period will be calculated as the mean of the scores reported between timepoints detailed in Section 14.3.3.
Composite VAS scores

VAS scores (individual and composite)

- Two separate composite VAS scores will be derived using the final VAS scores:
- Composite of nasal obstruction, nasal discharge, mucus in the throat and loss of smell

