 - CCI [REDACTED]
- Composite of nasal obstruction, nasal discharge, mucus in the throat, loss of smell and facial pain
 - CCI [REDACTED]

Nasal Surgery (reported on the disease related events page of the eCRF)
Time to first nasal surgery

 Calculated as (Date of first nasal surgery – Date of first dose of study treatment) + 1 Analysis excluding data from the follow-up period after Week 52: For participants who withdraw from the study before Week 52 and before experiencing surgery, event times will be censored at the time of study withdrawal For participants who complete to Week 52 without experiencing surgery, event times will be censored at the time of the Week 52 visit. Analysis including data from the follow-up period after Week 52: For participants who withdraw from the follow-up period before completion and before experiencing surgery, event times will be censored at the time of study withdrawal. For participants who complete the follow-up period without experiencing surgery, event times will be censored at time of completion of follow-up.
Need for surgery

 Need for surgery at Week 52 is based on the overall VAS symptoms score and the endoscopic NP score (centrally read). Participants will be classified as having a need for surgery if they meet the following: 
 Overall VAS symptoms score >7 (Weeks 49-52) and total endoscopic NP score ≥5 (Week 52, centrally read) Participants who have undergone nasal polyps surgery at any time prior to the week 52 visit, or who have a missing endoscopic NP score (centrally read) at Week 52, or missing overall VAS symptom score (Weeks 49-52) will be identified for analysis as still having a need for surgery.
Rate of surgery

 The crude rate of surgery will be presented for each treatment arm, this will be calculated as: $\left(\frac{\text{Total number of nasal surgeries}}{\text{Total number of days in the study}} \right) * 365.25$

Systemic steroid use
Conversion of glucocorticoid dose to mgs of prednisolone equivalent OCS use

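### The follow-up score tables (2.63 to 2.65) show only worst-value-filled data, so attrition after Week 52 pulls the mean change toward relapse and no display separates the two

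*SAP*

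**What the plan says.** SAP 7.5 lists the follow-up summaries and says of their data: "All data reported by these participants for the duration of their time in the study will be included in these summaries". It goes on to say that this covers time before and after entry to follow-up. It does not mention replacing missing scores.

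The replacement appears in the list of displays (SAP 14.12.6). Tables 2.63 (NP score) and 2.64 (VAS scores) carry "Programming Note: summaries from dataset with assigned values for subjects with surgery/missing data"; Table 2.65 (SNOT-22) has the same note with sinuplasty added.

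The fill is defined in SAP 14.6.5. For participants without surgery/sinuplasty who leave the study, the worst observed score is "assigned for all missing visits (or 4-week periods) following study withdrawal", and "The assigned value will be the worst observed value from baseline up until study withdrawal". For other gaps, "Subjects with missing data for other reasons will have their worst observed score (or worst observed 4-week mean) prior to the missing visit" assigned. Neither rule stops at Week 52. Change from baseline is "Post-Dose Visit Value – Baseline" (SAP 14.6.4).

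The list of displays has no observed-score follow-up table. The follow-up efficacy figures (2.23 to 2.25) are two Kaplan-Meier plots and blood eosinophils.

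**The concern.** The objective is maintenance of response after stopping mepolizumab. A worst-value fill is a defensible penalty in a Week 52 superiority comparison. In a descriptive table about durability, it gives a participant who still has the response but stops attending the same entry as one who has relapsed. Losses accumulate over Weeks 60, 68 and 76, so the filled share grows with time and can produce a downward drift that resembles waning effect. A reader of the tables cannot tell how much of a drift is observed, and a reader of 7.5 would not know that any of it is assigned.

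**Working it through.** The plan states no follow-up attrition and no calculation for the 200-participant follow-up, so there is no figure to reproduce. Attrition, SDs and full maintenance below are assumptions.

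1. **Which rule applies.** In the time-to-surgery derivation, SAP 14.6.5 treats leaving follow-up as study withdrawal: "For participants who withdraw from the follow-up period before completion and before experiencing surgery, event times will be censored at the time of study withdrawal". Protocol 6.4 counts the study as completed at Visit 15, so one could instead class the gap as missing for another reason. Either way it is filled. The difference is that the withdrawal rule names baseline as the start of the look-back and the other rule does not.

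2. **Sign of the filled change.** Higher is worse on all three instruments. With baseline B among the candidates, the worst value W satisfies W ≥ B, so W − B ≥ 0. For VAS, baseline is a 7-day mean and later values are 4-week means; the inequality is exact if the baseline mean counts as a candidate, as the text implies.

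3. **Arm mean.** Displayed mean = (1 − d) × M + d × F, where M is the maintained mean change, d the fraction missing and F ≥ 0 the mean filled change. For scale, take M = −1.2, rounded from the Phase II between-arm NP difference of −1.21 (protocol 3.1). At the most favourable F = 0, the display is −1.14, −1.08, −0.96 and −0.84 for d = 5%, 10%, 20% and 30%.

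4. **Simulation A.** Integer NP score 0-8, endoscopy schedule to Week 76, mean response −1.2 on mepolizumab and 0 on placebo, between-subject SD 1.5, visit noise SD 0 to 0.8, response fully maintained, dropout random. The entry floor of 5 on baseline moves the maintained mepolizumab mean to −1.3 to −1.4. F was +0.15 to +0.66 on mepolizumab.

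| d | true → shown, no noise | true → shown, noise SD 0.8 | response removed |
|---|---|---|---|
| 5% | −1.31 → −1.24 | −1.42 → −1.31 | 5-8% |
| 10% | −1.30 → −1.16 | −1.43 → −1.22 | 11-15% |
| 20% | −1.31 → −1.02 | −1.42 → −1.00 | 22-30% |
| 30% | −1.31 → −0.87 | −1.41 → −0.78 | 34-45% |

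   Check of one cell: 0.80 × (−1.31) + 0.20 × 0.15 = −1.02.

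5. **Simulation B.** 100 per arm, maintained −2.0 on mepolizumab and about −0.55 on placebo, between-patient SD 1.2, assessment SD 0.6. Shown on mepolizumab: −1.66 at 15% missing (0.34/2.0 = 17% removed) and −1.54 at 20% (0.46/2.0 = 23%).

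6. **Arm difference at d = 20%.** Placebo is filled too. Simulation A, no noise: −1.31 − (−0.17) = −1.14 becomes −1.02 − (−0.04) = −0.98, a loss of 14%. Noise SD 0.8: −1.42 − (−0.29) = −1.13 becomes −1.00 − (−0.01) = −0.99, a loss of 12%. Simulation B: −1.45 becomes −1.25, a loss of 14%.

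7. **Median.** In A about 70% of mepolizumab participants have a change of −1 or better, so the median leaves −1 only when (1 − d) × 0.70 < 0.50, that is d above about 29%. In B, rerun with an assumed onset of effect, the displayed median stayed at −2 in about 80% of trials at 15% missing and 59% at 20%.

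8. **If relapsers leave more often.** Suppose 30% relapse fully, 70% hold −2.0, and relapsers drop out three times as often. The true mean is 0.70 × (−2.0) = −1.40. With dropout of 10% against 30%, observed scores give −2.0 × 0.63/0.84 = −1.50, and the fill gives no better than −2.0 × 0.63 = −1.26. With 15% against 45%: −2.0 × 0.595/0.76 = −1.57, and no better than −1.19. The two displays err in opposite directions.

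**The case against.** Two stronger readings are tempting, and the documents support neither.

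A reader might infer that 7.5 promises observed data and the tables break that promise. The sentence in 7.5 says which study periods enter, not whether gaps are filled. The SAP uses the same language for filled analyses: the opening of Section 7 speaks of data reported up to Week 52 for sections that contain the fill, and Tables 2.39, 2.44 and 2.51 carry that footnote beside the assigned-value note. Section 7.5 is silent, not contradictory.

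A reader might also infer that the tables will make a maintained response look lost. That is true of each filled participant but not of the table: 70% or more of the mean response remains at 15-20% missing, the median holds better, and SAP 14.5.2 has both displayed. Both arms are filled. Only losses after entry to follow-up count, because non-entrants are outside the follow-up population. Early-withdrawal data are reassigned to a scheduled visit, and isolated diary gaps do not trigger a fill because VAS periods average whatever was reported.

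The strongest point concerns the remedy. Observed scores flatter durability if relapsers leave (step 8), and switching rule at Week 52 could create a false improvement at Week 60. This stands, and it is why the fill should not simply be replaced.

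Attrition is reported in Tables 1.4 and 1.5, and analysis datasets will flag imputed values. That helps, but a disposition table does not let a reader undo the fill. Table shells are not public, so whether n assigned is shown cannot be judged.

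**Conclusion.** The point holds as a bias in proportion to attrition, with nothing listed to expose it. Every score filled after withdrawal from follow-up gives a change of zero or worse. Under assumed inputs, this removes about 17-30% of a fully maintained mepolizumab mean response at 15-20% missing, and about 12-14% of the arm difference at 20%. The size depends on assumed attrition, effect and variability for the NP score; VAS and SNOT-22 were not quantified. Losses would be small if attrition is near 5%. The tables are descriptive and outside the testing hierarchy, so no test, alpha or sample size is affected. What is at stake is whether the trial can describe durability without confusing relapse with absence.

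**What to change.** - In SAP 7.5, state that Tables 2.63 to 2.65 use the assigned values of 14.6.5, and say whether leaving follow-up counts as study withdrawal for that rule.
- In each of the three tables, keep the assigned-value panel and add a second one. The new panel applies one rule at all visits, before and after Week 52: assign values only after surgery/sinuplasty, otherwise summarise observed scores.
- Show n observed and n assigned or missing by visit and arm.

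The cost is one short addition to the text and three extra panels; the planned imputation flags in the analysis datasets already supply the counts. The observed panel rests on participants still attending and may be optimistic, so a footnote should say that the two panels are to be read together.
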